### **5.2.** Selection of Study Population

Subjects will be screened and the data collected will be reviewed by the principal investigator. Only those subjects who meet all of the eligibility criteria will be enrolled.

#### 5.2.1 Inclusion Criteria

Subjects who meet all of the following inclusion criteria will be eligible to participate in the study:

- 1. Subject signs an institutional review board (IRB)-approved written informed consent and privacy language as per national regulations (e.g., Health Insurance Portability and Accountability Act authorization) before any study-related procedures are performed.
- 2. Subject is a healthy man or woman, 18 to 60 years of age, inclusive, who has a body mass index of 18.5 to 29.9 kg/m^2, inclusive, at Screening.
- 3. Subject has normal medical history findings, clinical laboratory results, vital sign measurements, 12-lead electrocardiogram (ECG) results, and physical examination findings at Screening or, if abnormal, the abnormality is not considered clinically significant (as determined and documented by the investigator or designee).
- 4. Subject must have a negative test result for alcohol and drugs of abuse at screening and Check-in (Day 0)
- 5. Subject has no known or suspected allergies or sensitivities to any components of the sunscreen formulation.
- 6. Female subjects must be of nonchildbearing potential or, if they are of childbearing potential, they must: 1) have been strictly abstinent for 1 month before Check-in (Day 0) and agree to remain strictly abstinent for the duration of the study and for at least 1 month after the last application of study drug; OR 2) be practicing 2 highly effective methods of birth control (as determined by the investigator or designee; one of the methods must be a barrier technique) from at least 1 month before Check-in (Day 0) until at least 1 month after the last application of study drug.
- 7. Female subjects must not be pregnant or lactating before enrollment in the study.

- 8. Male subjects must agree to practice 2 highly effective methods of birth control (as determined by the investigator or designee; one of the methods must be a barrier technique) from at least 1 month before Check-in (Day 0) until at least 1 month after the last application of study drug.
- 9. Subject is highly likely (as determined by the investigator) to comply with the protocol-defined procedures and to complete the study.

Note: subjects with any skin type or skin pigment type may be eligible for the study.

### **5.2.2** Exclusion Criteria

Subjects who meet any of the following exclusion criteria will not be eligible to participate in the study:

- 1. Subject has broken, irritated, or unhealed skin.
- 2. Subject has an active sunburn.
- 3. Subject has used a tanning bed in the previous 4 weeks.
- 4. Subject has known skin or autoimmune disease(s).
- 5. Subject is anemic or has any chronic condition(s) that may impact blood sample collection.
- 6. Subject has any underlying disease or surgical or medical condition (e.g., cancer, human immunodeficiency virus [HIV], severe hepatic or renal impairment) that could put the subject at risk or would normally prevent participation in a clinical study.
- 7. Subject has known or suspected allergies or sensitivities to any components of the sunscreen formulation.
- 8. Subject has clinical laboratory test results (hematology and serum chemistry) at Screening that are outside the reference ranges provided by the clinical laboratory and considered clinically significant by the investigator.
- 9. Subject has a positive test result at Screening for HIV 1 or 2 antibody, hepatitis C virus antibodies, or hepatitis B surface antigen.
- 10. Subject is unable or unwilling to undergo multiple venipunctures for blood sample collection because of poor tolerability or poor venous access.
- 11. Subject has received or applied the topical sunscreen formulations used in the current study, or any other product containing the active ingredients of the topical sunscreen formulations used in the current study, within 7 days before Check-in (Day 0).

- 12. Subject has used any personal care product(s) containing any active sunscreen ingredient, such sunscreen products, hand or body moisturizing lotion, makeup or foundation, lip balm, or lipstick, within 7 days before Check-in (Day 0).
- 13. Subject is unable or unwilling to tolerate the scent of sunscreen for the duration of the treatment period.

### **5.3.** Screening Failures

Subjects who sign and date the informed consent form but who fail to meet the inclusion and exclusion criteria are defined as screening failures. A screening log, which documents the subject initials and reason(s) for screening failure, will be maintained by the investigator for all screening failures. A copy of the log should be retained in the investigator's study files.

If a subject fails the screening process because of an abnormal laboratory result, they can receive a copy of the results upon request. The investigator will determine if follow up for the abnormal laboratory result is needed, and will encourage the subject to follow up with his or her personal physician as appropriate. All subjects will be informed as to the reason(s) they are excluded from study participation, even if follow up is not required. If a subject fails the screening process because of a positive test result for human immunodeficiency virus or hepatitis, the positive result will be reported to local health authorities as required by law.

# 5.4. Termination of Study or Investigational Site

# 5.4.1 Criteria for Termination of the Study

The study will be completed as planned unless one of the following criteria is satisfied that requires early termination of the study:

- New information regarding the safety or efficacy of the study product(s) that indicates a change in the known risk profile for the study drug(s), such that the risk is no longer acceptable for subjects participating in the study.
- Significant violation of Good Clinical Practice (GCP) that compromises the ability to achieve the primary study objective or compromises subject safety.

# 5.4.2 Criteria for Termination of Investigational Site

The study site may be terminated if the site (including the investigator) is found in significant violation of GCP, the protocol, the contractual agreement, or is unable to ensure adequate performance of the study.

In the event that the sponsor elects to terminate the study or the investigational site, a study-specific procedure for early termination will be provided by the sponsor; the procedure will be followed by the applicable investigational site during the course of termination.

### 5.5. Criteria for Subject Withdrawal

Subjects may withdraw from the study at any time at their own request, or they may be withdrawn by the investigator without the approval of the subject based on the investigator's clinical judgment. A subject is not required to provide a written request to withdraw from the study; however, a written request is required if a subject withdraws consent for his or her personal data to be used for study-related purposes.

A subject may be discontinued for any of the following reasons:

- AE: The subject has experienced an AE that, in the opinion of the investigator, requires early termination. The appropriate electronic case report form (eCRF) must be completed for each AE. If a subject is discontinued from the study due to an AE, the investigator is required to follow up with the subject until the event resolves or becomes stable. If a subject dies during the study, the cause of death must be reported as a serious AE (SAE), with an outcome of death noted in the eCRF.
- Protocol Violation: The subject failed to meet protocol entry criteria or did not adhere to protocol requirements, and continued participation poses an unnecessary risk to the subject's health.
- Withdrawal by Subject: The subject (or other responsible individual [e.g., caregiver]) wishes to withdraw from the study in the absence of a medical need.
  - NOTE: Withdrawal due to an AE should not be recorded in the "voluntary withdrawal" category.
- Study Terminated by Sponsor: The sponsor, IRB, FDA, or other regulatory agency terminates the study.
- Pregnancy: The subject is found to be pregnant.
  - NOTE: If the subject is found to be pregnant, the subject must be withdrawn immediately. The pregnancy will be followed up to term, and the outcome, including any premature termination will be recorded. All live births must be followed for a minimum of 30 days or until the first well baby visit.
- Other.

NOTE: This category records withdrawals caused by an accidental or a medical emergency, unblinding, and other rare cases. The specific reason should be recorded in the comment space of the eCRF.

## 5.5.1 Handling of Withdrawals

The investigator may terminate a subject's study participation at any time during the study when the subject meets the criteria described in Section 5.5. In addition, a subject may discontinue his or her participation without giving a reason at any time during the study. Subjects will be informed that their participation in the study is voluntary, that refusal to participate will involve no penalty or loss of benefits to which the subject is otherwise entitled, and that the subject may discontinue participation at any time without penalty or loss of benefits to which the subject is otherwise entitled.

Should a subject's participation be discontinued, the primary reason for termination must be recorded. In addition, efforts should be made to perform all procedures scheduled for the early termination visit. Any data and samples collected before subject withdrawal will become the property of the sponsor.

### **5.5.2** Replacement Subjects

Approximately 72 healthy subjects are planned for enrollment, of which 24 subjects will be enrolled and randomized in Part 1 and 48 subjects will be enrolled and randomized in Part 2. Up to 18 subjects may be qualified as replacements. Thus, a maximum of 90 subjects may be exposed to study drugs and procedures during the study.

# 5.6. Study Visits

#### 5.6.1 Recruitment

Recruitment materials (e.g., internet, radio, and print advertisements, social media posts) will be approved by the local IRB before telephone screening. The sponsor is responsible for registration of the study on clinicaltrials.gov; however, this may not occur until the IRB has approved the final study protocol.

# 5.6.1.1 Compensation

Subjects will be offered payment for Screening; however, if the results of their alcohol and drug screening tests are positive, they will not be compensated. Subjects who complete the entire study (Day 0 to Day 7 in Part 1 or Day 0 to Day 21 in Part 2) will receive payment according to the schedule provided in the informed consent form. No special incentives are offered. Final payment will not be released until all follow-up procedures have been completed and accepted by the investigator.

If a subject chooses to withdraw from the study prematurely, he or she will only be compensated for completed days. If subjects are withdrawn for medical reasons or if the study is halted temporarily or permanently, the subjects will receive compensation proportional to the time spent in the study. No compensation will be provided if a subject is dismissed from the study for noncompliance (e.g., improper conduct, ingesting alcohol and/or drugs [including recreational drugs], tampering with the study drug, consuming any prohibited foods or beverages).

If subjects are required to stay in the clinic for a longer period for safety reasons, they will be compensated at a rate proportional to the entire compensation for the study. If a subject becomes ill or physically injured because of participation in this study, the subject will be referred for treatment.

## 5.6.2 Screening

The following procedures and assessments will be performed at Screening (Day -30 to Day -1):

• Obtain informed consent/HIPAA authorization (The informed consent process will be performed by a clinical research nurse in a private room. The subject will be given unlimited time to ask questions regarding study participation, and each subject will be questioned to ensure their understanding.)

After informed consent is obtained:

- Review inclusion/exclusion criteria to confirm subject eligibility
- Record demographic information
- Measure height, weight, and calculate body mass index
- Perform serology screening (hepatitis B surface antigen, hepatitis C virus antibodies, and HIV antibody 1/2 antigen/antibody combination test)
- Record medical history, including social history and smoking habits
- Perform drug and alcohol screening (amphetamines, barbiturates, benzodiazepines, cannabinoids, cocaine, alcohol, opiates, phencyclidine, propoxyphene, and methadone)
- Perform a serum pregnancy test (female subjects only)
- Record prior medications
- Monitor for AEs
- Perform clinical laboratory tests (hematology, serum chemistry, and urinalysis)

- Measure vital signs (blood pressure, heart rate, respiratory rate, and oral body temperature)
- Perform a safety 12-lead ECG
- Perform a complete physical examination

## **5.6.3 Study Periods**

Part 1 and Part 2 of this study are open-label, randomized, 4-arm designs. Part 1 of the study has 1 treatment period and 3 follow-up days; subjects stay in the clinic for the full treatment and follow-up period. Part 2 of the study has 1 treatment period and 6 follow-up days; subjects stay in the clinic for the full treatment period and the first 3 follow-up days (total of 7 days) and will then return to the clinic for one-day visits on the subsequent 3 days of follow-up (Day 10, 14 and 21).

### 5.6.3.1 Check-in

The following procedures and assessments will be performed at Check-in (Day 0) as outlined in Appendix A: Schedule of Events:

- Review inclusion/exclusion criteria to confirm subject eligibility
- Perform drug and alcohol screening (amphetamines, barbiturates, benzodiazepines, cannabinoids, cocaine, alcohol, opiates, phencyclidine, propoxyphene, and methadone)
- Perform a serum pregnancy test (female subjects only)
- Perform Fitzpatrick skin type assessment
- Admit subject to the study clinic
- Randomization (after completion of check-in procedures on Day 0 or just before dosing on Day 1)
- Record concomitant medications
- Monitor for AEs

#### **5.6.3.2** Treatment

The following procedures and assessments will be performed during the treatment period (Days 1 through 4) according to the Schedule of Events (Section 10.1):

- Measure vital signs (blood pressure, heart rate, respiratory rate, and oral body temperature) before dosing
- Collect PK blood sample (10 mL) before and after dosing (see Section 5.7)

- Application of topical sunscreen for Part 1 at approximately 0900 hours and again at 2, 4, and 6 hours after the first dose. Application of topical sunscreen for Part 2 at approximately 0900 hours on Day 1 and again at approximately 0900 hours on Days 2, 3 and 4 followed by an additional 3 applications at 2, 4, and 6 hours after the first dose on Days 2, 3 and 4.
- Physical examination of skin at the sites of topical application for signs of irritation
- Record concomitant medications
- Monitor for AEs

### **5.6.3.3** Washout

Not applicable.

### **5.6.4** Discharge (or Early Termination)

The following procedures and assessments will be performed before the subject is discharged from the study or upon early termination:

- Measure vital signs (blood pressure, heart rate, respiratory rate, and oral body temperature)
- Physical examination of skin at the sites of topical application for signs of irritation
- Record concomitant medications
- Monitor for AEs
- Discharge subject from the study clinic after completion of all study procedures

# 5.6.5 Follow-up

The following procedures and assessments will be performed on Days 10, 14 and 21 for Part 2:

- Measure vital signs (blood pressure, heart rate, respiratory rate, and oral body temperature)
- Collect PK blood samples (10 mL) after dosing as follows:
  - o Day 10: 216 hours after first dose on Day 1 (Part 2 only)
  - o Day 14: 312 hours after first dose on Day 1 (Part 2 only)
  - o Day 21: 480 hours after first dose on Day 1 (Part 2 only)
- Physical examination of skin at the sites of topical application for signs of irritation
- Symptom-directed brief physical examination at the investigator's discretion

- Record concomitant medications
- Monitor for AEs

# **5.7.** Study Procedures

### 5.7.1 Pharmacokinetic Assessments

### 5.7.1.1 Pharmacokinetic Sample Collection

Pharmacokinetic blood samples (approximately 10 mL per sample) will be collected for determination of avobenzone, oxybenzone, octocrylene, ecamsule, homosalate, octisalate and octinoxate plasma concentrations (where applicable to the different sunscreen formulations) at the following time points (the time limit for PK sample draws can be +/-5 minutes from the nominal time):

- Day 1: 0 and 0.5, 1, 1.5, 2, 3 (Part 2 only), 4, 6, 8, 9, 10, 12, and 14 hours after initial dose
- Day 2: 23, 28, 33 h
- Day 3: 47, 52, 57 h
- Day 4: 71, 73, 74, 76, 78, 81, 82, 84 and 86 h
- Day 5: 95 hours
- Day 6: 120 hours
- Day 7: 144 hours
- Day 10: 216 hours (Part 2 only)
- Day 14: 312 hours (Part 2 only)
- Day 21: 480 hours (Part 2 only)

NOTE: when a time point corresponds with sunscreen administration, the PK sample will be collected before sunscreen administration.

# 5.7.1.2 Tape Stripping Sample Collection

For Part 2 only, tape stripping of the lower back to an area of around 3.8 cm^2 will be conducted once on Days 7 and 14 to determine residual sunscreen active ingredients in the superficial layers of the skin. Tape stripping will be applied to different areas of the lower back on Day 7 vs. Day 14 to prevent false sampling.

The area on the lower back for each subject will be marked with a skin marker. Before executing the tape stripping, hair on the marked area will be removed with the 3M trimmer (no razors as this would damage the skin and could lead to false sampling). A pre-weighed standard tape (Standard D-Squame ® adhesive tape) will be applied to a marked area under constant pressure of 225 g/cm^2 for 5 seconds using a D-Squame ®

Pressure device. The tape will be removed swiftly and placed in a standard tape rack after weighing. Tape stripping will be performed 6 additional consecutive times in the same area with sampling intervals of  $1 \pm 0.5$  minutes.

# 5.7.1.3 Pharmacokinetic Specimen Handling

The PK blood samples (10 mL each) will be collected into tubes containing K2EDTA, inverted several times to mix the blood with the anticoagulant, and placed in an ice bath. Within 30 minutes of collection, the samples will be centrifuged for 10 minutes, at 3000 revolutions per minute, at 4°C, by a study team member.

The plasma will be separated using a disposable plastic pipette and approximately half of the plasma will be transferred into duplicate cryotube vials labeled as Aliquot A (primary) and Aliquot B (backup). The plasma samples will be appropriately labeled and stored frozen at  $-70^{\circ}$ C or below until shipment. Temperature monitoring logs should be maintained and accessible for review by the study monitor.

The Aliquot A samples (primary) will be shipped first, on dry ice, to the bioanalytical laboratory at FDA for processing when requested by the sponsor. The Aliquot B samples (backup) will be held for a second shipment at a time after the completion of all Aliquot A sample shipment(s) and the timing of the Aliquot B shipment communicated by the sponsor. None of the PK blood samples will be stored at clinical facility for future use, however the sponsor will store them for analytical purposes of this study only.

The tape strips will be transferred to pre-labeled D Squame  $\mathbb{R}$  standard storage cards and stored frozen at  $-70^{\circ}$ C or below until shipment.

Both plasma and skin concentrations of avobenzone, oxybenzone, ecamsule, octocrylene, homosalate, octisalate and octinoxate (where applicable) will be assayed using a validated liquid chromatography with tandem mass spectrometry method.

### **5.7.1.4** Pharmacokinetic Parameters

The following PK parameters will be determined for each subject for each active ingredient:

### Across all study days (Primary Endpoint)

• Maximum concentration (observed peak drug concentration) (Cmax)

#### Days 1

- Maximum concentration (observed peak drug concentration) (Cmax)
- Time at which  $C_{max}$  occurs  $(T_{max})$

• AUC from time 0 to the sampling time corresponding to the last quantifiable concentration (Clast) (AUC0-t), calculated by the mixed linear logarithmic trapezoidal method

### Days 2 and 3

- Residual drug concentration (predose level) (Ctrough)
- 3 h post dose concentration

### Day 4

- Elimination rate constant (Kel), obtained by linear regression of the log-linear terminal phase of the concentration-time profile using at least 3 data points, excluding Cmax, otherwise Kel will not be determined. The acceptability criteria for determination of Kel will be a coefficient of regression more than or equal to 0.98.
   When Kel will not be determined, AUC0-inf and t1/2 will not be reported.
- Terminal half-life  $(t_{1/2})$ , calculated using the equation  $\ln 2/k$  after the last study drug application (on Day 4)
- Accumulation ratios, calculated using the following formula:

$$R_1 = AUC_{0-23} Day 4 / AUC_{0-23} Day 1$$

• AUC from time 0 extrapolated to infinity (AUC0-inf), calculated by the mixed linear-logarithmic trapezoidal method as:

$$AUC_{0\text{-inf}} = AUC_{0\text{-t}} + C_{last} / K_{el}$$

When the extrapolation represents more than 20%,  $AUC_{0-inf}$  and  $t_{1/2}$  will not be reported.

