# Pharmacokinetic Assessments:

Pharmacokinetic blood samples (approximately 10 mL per sample) will be collected for determination of avobenzone, oxybenzone, octocrylene, ecamsule, homosalate, octisalate and octinoxate plasma concentrations, where applicable to the different sunscreen formulations, at the following time points:

- Day 1: 0 and 0.5, 1, 1.5, 2, 3 (Part 2 only), 4, 6, 8, 9, 10, 12, and 14 hours after initial dose
- Day 2: 23, 28, 33 h
- Day 3: 47, 52, 57 h
- Day 4: 71, 73, 74, 76, 78, 81, 82, 84 and 86 h
- Day 5: 95 hours
- Day 6: 120 hours
- Day 7: 144 hours
- Day 10: 216 hours (Part 2 only)
- Day 14: 312 hours (Part 2 only)
- Day 21: 480 hours (Part 2 only)

NOTE: when a time point corresponds with sunscreen administration, the PK sample will be collected before sunscreen administration.

The following PK parameters will be determined for each subject for each sunscreen active ingredient:

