# 5. Investigational Plan

# 5.1. Study Design

This will be a single clinical study conducted in 2 parts. The duration of study participation will be approximately 37 days for part 1, including a 30-day screening period, a 4-day treatment period (Days 1-4) and subjects leaving the clinic on the morning of Day 7 following completion of scheduled End-of-Study activities. For part 2, the duration of participation will be approximately 51 days, including a 30-day screening period, a 4-day treatment period (Days 1-4) and subjects leaving the clinic on the morning of Day 7. Subjects in part 2 will then return to the clinical for follow-up visits on Days 10, 14 and 21 after which End-of-Study activities will be completed.

#### 5.1.1 Part 1

Part 1 is an open-label, randomized, 4-arm pilot study to evaluate the effects of multiple applications of 4 different topical sunscreen formulations in healthy adult subjects. Each arm will include 6 subjects (3 male and 3 female) with 1 formulation. A total of 24 subjects (12 male and 12 female) from all 4 arms will be admitted to the clinical research unit (CRU) on Day 0.

On the morning of Days 1 through 4, subjects will receive a topical application of the study product at approximately 0900 hours. The study drug will be weighed in advance and applied by a qualified person from the study team. Subjects will then receive 3 more topical applications on the same day at 2, 4, and 6 hours after the first dose.

### 5.1.2 Part 2

Part 2 is an open-label, 4-arm-study to evaluate the pharmacokinetics of avobenzone, oxybenzone, octocrylene, homosalate, octisalate and octinoxate (Part 2 products will not contain ecamsule) after multiple applications of a topical sunscreen formulation in healthy adult subjects. Part 2 will include 48 subjects (24 male and 24 female) and 12 subjects in each arm (6 male and 6 female). One of the formulations in Part 2 will be selected based on the plasma exposure data from the pilot study (Part 1). In addition, 3 new formulations will be added.

On the morning of Days 1 through 4, subjects will receive a topical application of the study product at approximately 0900 hours. The study drug will be weighed in advance and applied by a qualified person from the study team. Subjects will only receive one application on Day 1. On Days 2, 3 and 4, subjects will receive an initial dose and 3 more topical applications on the same day at 2, 4, and 6 hours after the first dose.

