#### 5.1.4 Common Procedures

Details of study visits and study procedures are described in Section 5.6 and Section 5.7, respectively, and the overall Schedule of Events for both parts of the study is presented in Section 10.1.

In both parts of the study, approximately 2 mg of sunscreen per 1 cm² of body surface (calculation per method of Dubois) will be evenly applied 4 times per study day (except for a one-time application on the first day in part 2) to areas of the body typically exposed to the sun: face, ears, neck, torso, arms, and legs (approximately 75% of the body surface area). The antecubital areas will be avoided when applying the sunscreen due to potential contamination of the sites used for intravenous (IV) PK blood sample collection. The topical applications of the study drug will be administered with subjects in swim wear to simulate real world settings as well as for easy application. In addition to swim wear, subjects may wear scrubs in between applications and at other times throughout the day/night. Subjects are required to shower each morning after the first PK blood sample collection (and before the first sunscreen application for that day), but not at other times during the day. And, subjects should not use any personal care products which contain avobenzone, oxybenzone, ecamsule, octocrylene, homosalate, octisalate or octinoxate during the study.

Blood samples (approximately 10 mL per sample) will be collected for determination of avobenzone, oxybenzone, octocrylene, ecamsule, homosalate, octisalate and octinoxate (where applicable) plasma concentrations.

Safety evaluations will include adverse event (AE) monitoring, vital sign measurements, and physical examinations. All AEs reported by the subject or observed by the investigator or CRU staff will be recorded. Any AE reported after the informed consent is signed and before study drug application will be recorded as medical history.

Subjects will remain in the CRU after admission on Day 0 until discharge on the morning of Day 7. In Part 2, subjects will return to the clinic on Day 10, 14 and 21 for follow-up PK sampling (Days 10, 14 and 21) and tape stripping (Days 14).

Subjects are not allowed to use products containing any of the active ingredients from 7 days before check-in until completion of End-of-Study procedures.

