# **5.8.** Study Treatments

### **5.8.1** Treatments Administered

#### Part 1

- La Roche Posay (Cream), Anthelios SX Daily Moisturizer Cream, Face Sunscreen SPF 15 with Mexoryl SX
- Hawaiian Tropic (Lotion); Island Sport Ultra-Light High Performance Sunscreen, SPF 50
- Neutrogena (Spray), Ultra Sheer Body Mist SPF 45
- Banana Boat (Spray); Sport Performance Coolzone Continuous Spray Sunscreen, SPF 50

Approximately 2 mg of sunscreen formulation per 1 cm^2 of body surface will be applied topically 4 times per day for 4 days to approximately 75% of the body surface area.

#### Part 2

- Hawaiian Tropic (Lotion); Island Sport Ultra-Light High Performance Sunscreen, SPF
   50
- Neutrogena (Aerosol Spray), Ultra Sheer Body Mist SPF 100
- Supergoop (Non-Aerosol Spray), Sunscreen Mist with Vitamin C SPF 50
- Supergoop (Pump Spray), Sun Defying Sunscreen Oil with Meadowfoam SPF 50

Approximately 2 mg of sunscreen formulation per 1 cm^2 of body surface will be applied topically once on Day 1 and 4 times per day on Days 2-4 to approximately 75% of the body surface area.

The antecubital areas will be avoided when applying the sunscreen due to potential contamination of the sites used for IV PK blood sample collection.

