All data will be presented in data listings. Data from subjects excluded from an analysis population will be presented in the data listings but not included in the calculation of summary statistics. The number of subjects who enroll in the study and the number and percentage of subjects who complete each assessment will be presented. The frequency and percentage of subjects who withdraw or discontinue from the study and the reason for withdrawal or discontinuation will be summarized. Continuous demographic and baseline characteristic variables (age, height, weight, body mass index) will be summarized overall and by treatment using descriptive statistics (number of subjects, mean, standard deviation [SD], median, interquartile range [IQR], and minimum and maximum). The number and percentage of subjects in each class of categorical demographic and baseline characteristic variables will also be summarized.

5 Pharmacokinetic (PK) Analyses and Primary/Secondary Outcomes

The PK sampling schedule for this study is summarized in Appendix A. The following PK parameters will be determined for each subject in Part 1 and Part 2:

Across all study days

- Maximum concentration (observed peak drug concentration) (C_{\max})

Day 1

- Maximum concentration (observed peak drug concentration) (C_{\max})
- Time at which C_{\max} occurs (T_{\max})
- AUC from time 0 to the 23 hour time point (C_{last}) (AUC_{0-23})

Days 2 and 3

- Residual drug concentration (predose level) (C_{trough})
- Concentration 3 hours after the last dose of the day

Day 4

- Maximum concentration (observed peak drug concentration) (C_{\max})
- Time at which C_{\max} occurs (T_{\max})
- Elimination rate constant (K_{el}) and terminal half-life ($t_{1/2}$); calculated after final dose using all the available data up to last study sample (144 hours for Part 1; 432 hours for Part 2)
- AUC from time 71 to the 95 hour time point (AUC_{73-95})
- AUC from time 0 extrapolated to infinity ($AUC_{0-\text{inf}}$) and/or last observed time point

Day 5, 6, 7, 10 (Part 2 only), 14 (Part 2 only) and 21 (Part 2 only)

- Residual drug concentration (C_{trough})

The primary and secondary outcomes of this study are as follows:

Primary Outcome:

1. Maximum* Avobenzone concentration (C_{\max})

Secondary Outcomes:

1. Maximum* Oxybenzone concentration (C_{\max})
2. Maximum* Octocrylene concentration (C_{\max})
3. Maximum* Ecamsule concentration (C_{\max})
4. Maximum* Homosalate concentration (C_{\max})

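### In Part 2 the accumulation ratio R1 divides a four-application day by a one-application day, so it cannot separate accumulation from the change in schedule

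*Protocol*

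**What the plan says.** Protocol section 5.7.1.4 opens with "The following PK parameters will be determined for each subject for each active ingredient". Under Day 4 it defines the accumulation ratio as "R_1 = AUC_{0-23} Day 4 / AUC_{0-23} Day 1". Neither the lead-in nor the formula restricts R1 to one part or adjusts for the number of applications. The same section does mark other items as belonging to Part 2 only (the Day 10, 14 and 21 residual concentrations), so the missing restriction on R1 applies it to both parts.

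The two parts have different Day 1 schedules. In section 5.8.1, Part 1 product is "applied topically 4 times per day for 4 days" and Part 2 product is "applied topically once on Day 1 and 4 times per day on Days 2-4". Section 5.1.2 says the same of Part 2: "Subjects will only receive one application on Day 1".

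R1 appears nowhere else. The synopsis list (introduced by "The following PK parameters will be determined for each subject for each sunscreen active ingredient") omits it. So do the SAP section 5 parameter list (introduced by "The following PK parameters will be determined for each subject in Part 1 and Part 2") and the SAP's list of parameters to be summarised. The SAP has a Day 1 AUC from 0 to 23 h. Its Day 4 AUC starts at 71 h in words but carries the subscript 73-95.

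**The concern.** An accumulation ratio isolates carry-over only when the two days being compared receive the same regimen. Part 1 meets that condition and Part 2 does not. A Part 2 R1 above 1 could come from carry-over, from the three extra applications on Day 4, or from both, and the ratio cannot say which.

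If R1 is reported as defined, some or all of the schedule effect could be read as accumulation. The comparison most exposed is the Hawaiian Tropic lotion, which is arm B in Part 1 and arm E in Part 2. With identical kinetics, the two arms could show clearly different values under the same label.

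**Working it through.** The plan states no value for R1, so there is no figure to reproduce. The check has two steps: a count from the documents, then an illustration of size under stated assumptions.

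**Count of applications in each AUC window** (Protocol 5.1.1, 5.1.2, 5.8.1)

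- Part 1: 4 on Day 4 and 4 on Day 1, so 4/4 = 1.
- Part 2: 4 on Day 4 and 1 on Day 1, so 4/1 = 4.

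The confounding follows from this count alone and needs no model.

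**Illustration of size.** The assumptions are mine, because the documents give no half-lives: linear one-compartment kinetics, first-order absorption, and equal amount per application. Absorption half-lives are 2, 4, 6, 8 and 12 h, crossed with elimination half-lives of 6, 12, 24, 48 and 72 h (25 pairs). Each same-day re-application contributes a fraction f of that day's first application.

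The AUC from one unit application over the following x hours is

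G(x) = ka/(ka − ke) × [(1 − e^(−ke·x))/ke − (1 − e^(−ka·x))/ka].

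Applications at 0, 2, 4 and 6 h have 23, 21, 19 and 17 h inside the 23-hour window. With no carry-over between days, Part 2 R1 is therefore

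1 + f × [G(21) + G(19) + G(17)] / G(23).

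Worked case with absorption half-life 4 h and elimination half-life 12 h: G(23) = 10.595, G(21) = 9.819, G(19) = 8.968, G(17) = 8.040. At f = 1 this gives 1 + 26.827/10.595 = 3.53. The like-for-like value in Part 1 is 1.00.

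Now add carry-over for the same case by summing all applications over Days 1 to 4, with Day 4 taken as 72 to 95 h:

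- Part 1: 66.49/37.42 = 1.78.
- Part 2: 65.36/10.595 = 6.17.

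The Day 4 AUCs are almost equal (66.49 and 65.36). Nearly all of the difference comes from the Day 1 denominator.

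Ranges over the 25 pairs:

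| Contribution of each re-application (f) | Part 2 R1, no carry-over | Part 2 R1 ÷ Part 1 R1, with carry-over |
|---|---|---|
| 100% | 3.22–3.78 | 2.62–3.78 |
| 50% | 2.11–2.39 | 1.80–2.39 |
| 25% | 1.55–1.70 | 1.39–1.70 |
| 10% | 1.22–1.28 | 1.15–1.28 |
| 0% | 1.00 | 1.00 |

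**Sensitivity**

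- *Shorter half-lives.* With absorption 1 h and elimination 0.5 h, the quotient at f = 1 reaches 4.00. The 3.78 ceiling therefore belongs to the grid and is not a bound.
- *Morning shower.* Section 5.1.4 says "Subjects are required to shower each morning after the first PK blood sample collection". If the shower removed all unabsorbed product, an assumed extreme, the quotients would be 2.72–3.78, 1.86–2.39, 1.42–1.70 and 1.00 for f of 100%, 50%, 25% and 0%.
- *Planned sampling times.* With the protocol's mixed linear-log trapezoid and a 71–95 h window, the quotients are 2.60–3.73, 1.79–2.37, 1.39–1.68 and 1.00 for the same f. A 73–95 h window changes only the first lower limit, to 2.61.

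**SAP Day 4 window.** 95 − 71 = 24 h and 95 − 73 = 22 h, against 23 h on Day 1. At f = 1 on the same grid, the longer window gives an AUC 3.9% to 8.2% larger than the shorter one. This is a separate labelling problem that affects both parts. It does not drive the R1 result.

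**The case against.** The strongest reply is that the SAP does not plan this output. R1 is missing from both SAP lists and from the synopsis, so a confounded ratio may never be produced. That limits the reach but does not remove the problem. Section 5.7.1.4 still says R1 will be determined, and Protocol section 5.9.6 says PK parameters will be listed and summarised. The SAP's silence leaves the status of R1 open.

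A second reply is that the one-application Day 1 in Part 2 is stated openly and repeatedly, so an attentive reader would allow for it. This is fair: the documents support saying that R1 could be misread, not that it will be. Even a careful reader, however, could not recover the accumulation component from the ratio.

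A third reply is that Part 2 collects other data under one schedule on Days 2 to 4: troughs, concentrations 3 h after the last application on Days 2 and 3 (33 and 57 h), and an 81 h sample on Day 4. These do describe build-up without R1, but they still carry some influence from Day 1. On the assumed grid at f = 1, the 81 h/33 h ratio is 1.08–3.90 in Part 2 against 1.01–2.26 in Part 1, and the 95 h/47 h trough ratio is 1.06–2.59 against 1.00–1.84. They can serve within Part 2 but not for comparison between parts.

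Finally, the size is an assumption throughout. That stands. The quotient runs from 1.0 upward depending on how much re-applications add, and the documents do not say. The 4:1 against 4:4 count does not depend on it.

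**Conclusion.** The concern holds and is minor. As defined, R1 is an accumulation ratio by schedule in Part 1 but not in Part 2, where it combines one-versus-four applications with any carry-over. That conclusion rests only on the documents.

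The size rests on assumed linear kinetics, assumed half-lives and an unknown contribution from re-application. The inflation relative to Part 1 is roughly 2.6- to 3.8-fold on the main grid if re-applications are fully additive, and nil if they add nothing. There is no guaranteed floor above 1.0.

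The consequences are limited to how accumulation is described. Cmax across all study days and the rule for choosing the Part 2 product do not use R1.

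**What to change.** - **Protocol 5.7.1.4:** limit R1 to Part 1. Alternatively, keep the ratio in Part 2 under another name, as a combined schedule-and-accumulation ratio. Any version divided by amount applied should state that it assumes exposure proportional to amount.
- **Reporting:** do not pool or compare the ratio across parts, in particular between arms B and E. If a Part 2 descriptor of build-up is wanted, the planned Days 2 to 4 troughs and post-application concentrations can be used within Part 2 only, with a note that they still reflect the Day 1 schedule.
- **SAP section 5:** say whether R1 is reported. Reconcile the 71 h wording with the 73–95 symbol, and use one Day 4 window of the same length as the Day 1 AUC wherever a ratio is formed.

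The cost is one restriction or label in the protocol, and one corrected line plus one statement in the SAP. No new data and no change to the application schedule are needed. Limiting R1 to Part 1 gives up an AUC-based accumulation ratio in Part 2, but a one-application Day 1 could not supply a clean one.
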